1 INTRODUCTION / BACKGROUND & RATIONALE

incident pregnancy.

Hypertensive disorders complicate 6-12% of pregnancies (Khedagi and Bello 2021), leading to PE and intrauterine growth restriction (Di Martino et al. 2022). PE is more commonly associated with adverse maternal and foetal outcomes such as eclampsia, stroke, renal and hepatic dysfunction, foetal growth restriction and stillbirth. According to the most recent Confidential Enquiries into Maternal Death, PE is still one of the most common causes of direct maternal deaths in United Kingdom and is also associated with increased perinatal mortality and morbidity(Shennan et al. 2012). GH is increasing in line with elevated cases of obesity and diabetes in the population (Shah et al. 2008). This is becoming more critically relevant for maternity especially as the obese and diabetic population is increasing in the younger age groups during the reproductive. Hypertensive disorders in pregnancy account for 5% (1:20) of stillbirths with no congenital malformation. Importantly, women who develop PE are also at increased long-term risk of CV disease and stroke (Honigberg et al. 2022). The impact of increased risk of CV disease later in life is under appreciated. Predictions of pregnancies at risk of hypertensive pregnancy will allow stratification of women at most risk, for future and earlier follow up. In addition, this understanding will provide insight into pathological mechanisms. An understanding of when endothelial dysfunction occurs and if it preceeds gestational hypertension will be key to developing diagnostic stratification. Recent studies have suggested that arterial stiffness and endothelial dysfunction may be an important factor in development of GH. Similarly, myocardial impairment and chamber diastolic dysfunction was observed more frequently in GH (a severe form of GH compared with normal pregnancies. These changes in CV function may be present before the clinical onset of GH and are evident after delivery. Therefore, GH seems to be the expression of a

Biomarkers with cardiac ultrasound at peripartum period (before delivery and within a week of giving birth) show a close connection between the endothelium indicators utilised in hypertensive pregnancy diagnosis and severity indication (Giorgione et al. 2023). Retinal imaging and subsequent Al analysis has been successfully used to assess changes in the microvascular system related to endothelial dysfunction in relation to stroke, Alzheimer's and type 2 diabetes (Cheung et al. 2021; Doney et al. 2022). However, retinal imaging has not been used extensively in hypertensive pregnancy diagnosis nor for the subsequent follow-up. Yet retinal imaging is a quick, easy and cost-effective technique to monitor endothelial health.

CV "syndrome" that exists before pregnancy, become evident during pregnancy, and puts women at risk of other serious adverse events after the

In our study, application of retinal imaging and subsequent analysis technology will be used to assess endothelial function during gestation and the subsequent follow up. Moreover, the application of retinal imaging and subsequent analysis technology in assessing endothelial function during gestation presents a novel approach with the potential to provide valuable insights into the microvascular changes associated with gestational endothelial dysfunction, offering a non-invasive method for monitoring maternal vascular health.

2 STUDY OBJECTIVES & OUTCOMES

To establish vascular changes in retinal and ophthalmic Doppler in normal and pregnancies associated with gestational hypertension. We hypothesise that women with GH or foetal growth restriction will have increased endothelial dysfunction, as shown by retinal and ultrasound imaging.

Table 1: Primary Objectives and Outcome Measures

Primary Objective:	Outcome Measure:	Timepoint of outcome measured
Objective: To investigate the potential of retinal imaging technology to assess endothelial function in women during pregnancy, in order to evaluate the effect of GH on maternal CV function.	 Retinal imaging Biomarkers of Endothelial Function Ultrasound Pulse- Wave Doppler 	mild-late pregnancy for women with GH and normal pregnancies.

Table 2: Secondary Objectives and Outcome Measures

Secondary Objective:	Outcome Measure:	Timepoint of outcome measured
Study - Aim: A prospective study to image the retina in early and mid-stages of gestation and track pregnancy outcome in correlation with serum biomarkers and standard diagnostic measurement (ultrasound pulse-wave doppler) imaging.	 Retinal imaging Biomarkers of Endothelial Function Ultrasound Pulse- Wave Doppler 	mild-late pregnancy for women with GH and normal pregnancies.

3 STUDY DESIGN

The study design is a prospective study, as it examines endothelial function in pregnant women and see how this relates to the potential development of gestational hypertension.

Study Aim: Imaging the retina in mid-stages of gestation and tracking pregnancy outcomes in correlation with serum biomarkers and for standard diagnostic measurement (ultrasound pulse-wave Doppler) imaging.

 Pregnant women will be recruited at the normal pre-natal visits (early and mid gestation scans)

- Blood samples will be taken in addition to bloods take in line with routine care (early 10-12 week scan). 20-week scan women will be requested to provide blood samples. (sFlt-1 &PLGF (clinically used to diagnose PE), endothelin-1 (marker of endothelial dysfunction))
 - Recruit women who are pregnant and follow pregnancy outcome
 - Recruit women who have gestational hypertensionGH and gestational-matched normal tensive women for CV assessment.
 - Endothelial CV assessment.
 - Retinal imaging
 - Blood sample (sFlt-1 &PLGF (clinically used to diagnose PE), endothelin-1 (marker of endothelial dysfunction))
 - Ultrasound
 - Carotid
 - Ophthalmic artery doppler

3.1 INTERVENTION

- Retinal imaging
- Blood sample (sFlt-1 &PLGF (clinically used to diagnose PE), endothelin-1 (marker of endothelial dysfunction))
- Ultrasound
 - Carotid
 - Ophthalmic artery doppler

Retinal imaging and ultrasound (including carotid and ophthalmic artery Doppler) will be conducted in the Tayside Clinical Research Centre/Clinical room at the Division of Cardiovascular Research (Blood Flow Lab), Ninewells Hospital, by PI, [name].

Blood samples will be collected by nurses in the Clinical Research Centre (CRC). All procedures will be completed on the same day as the examination.

3.2 STUDY RECRUITMENT

Women will be recruited who are pregnant for assessment in mid and/or late term. The outcome of the pregnancy will be tracked.

Women will be invited to join the study by the care teams in clinics at Ninewells and the Tayside area

- Obstetric Antenatal Clinics (Recruitment will be overseen [name] [name] (UoD/NHS) and [name] (NHS))
- Assisted conception clinic (Recruitment will be overseen [name] [name] (UoD/NHS))
- Hypertension Clinic (Recruitment will be overseen by [name](UoD/NHS))

This is a prospective study. Control groups will be made up of women that do not get gestational hypertension. Pregnant women that attend the Hypertension clinic may be recruited due to their gestational hypertension. Women attending the Obstetric Antenatal Clinics and Assisted conception clinics will be identified with clinical collaborators including [name] [name], [name] and [name]. To be able to identify potential participants from their medical records Caldicott Approval will be sought. Only with Caldicott approval will the medical records be searched.

The care team will approach or invite participation in the study in clinic. Any invitation will introduce the potential patient to the study team and will include a PIS. The care team will not follow up with patients to determine their interest in the study.

The study team will include Clinical Research Centre nurses that will assist with recruitment. The study team will confirm recruitment via a short telephone conversation prior to them attending Ninewells for the study visit.

Advertisement of the study and identification of potential participants will be identified from the NHS Tayside clinics at Ninewells Hospital including maternity clinics, ultrasound department, antenatal clinics, day assessment unit, Assisted Conception Unit, https://www.acudundee.org/ hypertension and diabetics clinics among others. Caldicott approval will be gained to allow identification of potential participants from medical records and clinical lists by the care team. Letters with PIS may be sent to the potential participants from the clinical team. We chose the following sites, since this is where pregnant women obtain their routine care.

The care team will approach or invite participation in the study either in clinic or via post/email. Any invitation will introduce the potential patient to the study team and will include a PIS will be written on behalf of the care team. The care team will not follow up with patients to determine their interest in the study. A researcher (study team) who is not in the care team can meet potential participant only with patient's permission (using a Reply slip). Or the patient contacts the study team directly using information from the PIS received from the care team

A minimum of 24 hours will be given prior to consent being obtained.

Women will be invited to join the study by the care teams in clinics at Ninewells and the Tayside area

- Assisted Conception Unit (Recruitment will be overseen [name] [name] (UoD/NHS))
- Obstetric Antenatal Clinics (Recruitment will be overseen [name] [name] (UoD/NHS) and [name] (NHS))
 - Hypertension Clinic (Recruitment will be overseen by [name](UoD/NHS))

[figure not shown]
3.3 STUDY DESCRIPTION

At the commencement of the study, the care team will approach pregnant women who meet the criteria. Pregnant women will get a Participant Information

Sheet (PIS) and can reach out to the study team if they wish to participate. Each participant is only required to attend a single visit, which will last roughly 1 hour.

Pregnant volunteers will be recruited at their first (10-12 week) and second (20 weeks) scans in line with their clinical care. In addition to their clinical ultrasounds, an ophthalmic and carotid artery ultrasound will be conducted. In addition a retinal scan and blood sample taken.

3.4 STUDY FLOWCHART

3.5 STUDY MATRIX

Example Study Matrix

	Recruitm ent	Week 10 (+/-3wk)	Week 20 (+/-3wk)
Recruitment	V1	n/a	n/a
Cardiovascular assessment		X	X
Blood sample		X	Χ
Blood processing		X	Χ

On the same day as the blood sample, carotid artery doppler, and retinal imaging, an ophthalmic artery Doppler will be conducted. In the unlikely event that this is not possible, the ophthalmic artery doppler will be finished in 7 days.

We aim to image women up to 2 times; at 10 and 20 weeks (+/- 3 weeks) in line with their routine clinical care. However, we will accept only one visit at either of the timepoints.

STUDY ASSESSMENTS

Retinal imaging

Retinal imaging is a basic ophthalmic imaging technique which takes a photo of blood vessels at the back of the retinal. The participant needs to open her eyes and stare straight ahead at an object while the image is taken and uploaded to a computer.

Doppler Ultrasound

The ultrasound is a painless, safe test that uses sound waves to make images of the region of interest. Two regions will be examined in this study, which are Ophthalmic and Carotid region.

OPHTHALMIC ARTERY DOPPLER

The participant will be positioned in a supine position and will rest for 5 minutes. Subsequently, an ultrasound probe with sterile conduction gel will be applied to her closed upper eyelid. A quick 2D scan will be undertaken to identify anatomical features of the eye, including the optic nerve, visible as a hypoechoic band, which will be utilised as a reference. The ocular artery will be identified using colour flow, specifically in the superior and medial regions of the artery, around 15 mm behind the optic disc. Subsequently, pulsed-wave Doppler will be employed to document three to five similar waveforms.

To reduce any potential negative impact on the eyes and adhere to the ALARA ("as low as reasonably achievable") guideline, the study will be conducted in under 2 minutes per eye. Both eyes will be imaged.

CAROTID ULTRASOUND

During the test, gel is applied to the side of the neck to help the sound waves travel effectively. While lying down, a small scanner is gently placed on the skin of the neck to take the necessary pictures. This procedure is safe and may cause some pressure, but not pain, as the device moves on the neck.

The elasticity of the blood vessels will also be measured. A small pen-like device will be placed gently on the neck and at the same time a cuff is placed on the thigh (over your clothes).

The test takes about 10 minutes.

Retinal imaging and ultrasound (including carotid and ophthalmic artery Doppler) will be conducted in the Tayside Clinical Research Centre/Clinical room at the Division of Cardiovascular Research (Blood Flow Lab), Corridor L, Level 7, Ninewells Hospital, by PI [name].

Blood Samples

A 20ml blood sample will be taken from the participant during the investigation/assessment. Which are (sFlts-1, PLGF and endothelin-1). The blood sample will be collected concurrently with their usual blood tests that are clinically necessary as part of their regular clinical care.

Studying Pregnancy's VAscular and Retinal Changes (SPARC), Non CTIMP Protocol (SPARC) During Preg <v1.0 13/3/2025>; IRAS: 347685

A 20ml blood sample will be taken from the participant during the investigation/assessment by trained CRC staff for study of circulating biomarkers. This is intended to be a Prospective study and will provide data for future power analysis to estimate how many women need to be recruited.

Blood samples will be collected by nurses in the Clinical Research Centre (CRC). All procedures will be completed on the same day as the examination.

Once all the measurements have been taken, there will be no further requirements or assessments. The research specific procedure results will be recorded in the CRF only.

Blood samples from both control and case will be used to assess circulating biomarkers for example but not limited to sFlt-1 & PLGF (clinically used to diagnose preeclampsia), endothelin-1 (marker of endothelial dysfunction).

Assessment will be conducted by UoD Immunoassay Biomarker Core Facility. Blood tests for cardiometabolic profiling may also be requested (via clinical laboratory, Clinical Research Centre/NHS Tayside) or collected from patient records with prior Caldicott Approval.

Samples will be stored in Division of Cardiovascular Research, School of Medicine, Ninewells low temperature freezers (-70oC).

Patient consent will be requested to store any surplus blood for future use which will require prior ethical approval.

3.6 CONSENTING PARTICIPANTS

The consenting of participants from the groups will be performed by the CI, PI or GCP trained delegated members of the study team competent in obtaining consent for research purposes.

3.7 INELIGIBLE AND NON-RECRUITED PARTICIPANTS

The reason(s) for ineligibility will be explained to participants and any questions they have will be answered. They will be thanked for their participation in screening.

3.9 STUDY SAFETY ASSESSMENTS

Pregnant women will undergo their standard care as routine. Research bloods, ultrasound and retina imaging will be obtained at the research site following informed patient consent. This usually will occur on the visit day in the clinical room at Division of Systems Medicine, Corridor L, Level 7, Ninewells Hospital. We do not envisage that any of these will interfere with their care or are likely to cause any harm. Nevertheless, any adverse events that may potentially be related to the study will be reported to the CI who will administer appropriate clinical action.

3.10 TISSUE

A blood sample will be collected on the examination day to conduct specific tests (sFlt-1 &PLGF and endothelin-1) and, with consent, will be stored for potential future use. Samples will be stored in Division of Cardiovascular Research, School of Medicine, Ninewells low temperature freezers (-70oC).

3.11 INCIDENTAL FINDINGS

Any incidental findings (IF: previously undiagnosed condition) considered to be clinically significant will be reported to the participant's GP and/or consultant by the CI or Site PI, with the consent of the participant.

3.12 STUDY POPULATION

Our study populations are defined as follows

The study design is prospective study. All pregnant women will be included at the start except for exclusion criteria see (3.15). Outcome of pregnancy will be documented and participants will be placed into one of two groups retrospectively:

3.13 NUMBER OF PARTICIPANTS

Study: 22 PARTICIPANTS
11 participants for case group
11 participants for control group

3.14 INCLUSION CRITERIA

Case group:

Women who

- Are Aged 18 or above
- Are Able to give written informed consent (ICF)
- Are in mid-to-late gestation.
- Were diagnosed with Gestational hypertension (systolic BP ≥ 140 mmHg or diastolic BP ≥ 90 mmHg) in their pregnancy.
- Do not have cardiac or ophthalmic disorders

Control group:

Pregnant women that are

- Aged 18 or above
- Able to give written informed consent (ICF)
- Have no gestational hypertension (normal pregnancy/ nonhypertension)
- Do not have cardiac or ophthalmic disorders

3.15 EXCLUSION CRITERIA

Exclusion criteria are the same for both case and control groups:

Case group:

Women who

- Women with ophthalmic disorders
- Women who have hypertension during pregnancy
- Maternal age less than 18 years at delivery.
- Women who are not capable of giving informed consent (ICF).
- Individuals participating in the clinical phase of another interventional study or have done so within the last 30 days (unless they are participating in the follow-up phase of another interventional trial/study, or who are enrolled in an observational study, will be co-enrolled where the CIs of each study agree)

Control group:

- Women with any history of gestational hypertension (systolic BP ≥ 140 mmHg or diastolic BP ≥ 90 mmHg))
- Women with ophthalmic disorders
- Women who had hypertension prior to pregnancy
- Maternal age less than 18 years at delivery.
- Women who are not capable of giving informed consent (ICF).
- Individuals participating in the clinical phase of another interventional study or have done so within the last 30 days (unless they are participating in the follow-up phase of another interventional trial/study, or who are enrolled in an observational study, will be co-enrolled where the CIs of each study agree).

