Primary	Objectives To investigate the potential of retinal imaging technology to assess endothelial function in women during pregnancy, in order to evaluate the effect of GH on maternal CV function.	Outcome Measures Primary Outcome Measures: 1. Retinal Vascular System 2. Endothelial Function 3. Cardiovascular Function biomarkers Secondary Outcome Measures: 1. Pregnancy-Related Health Outcomes 2. Maternal Health
Secondary	Objectives Study – Aim: Investigate whether retinal imaging is able to capture endothelial dysfunction in women who have complicated pregnancy. Endothelial function measured using retinal imaging and ultrasound pulse-wave Doppler and measured in correlation with serum biomarkers.	Outcome Measures 1. Primary Outcome Measures - Retinal Vascular Health measurements - Ultrasound Pulse-Wave Doppler Findings - Blood Biomarkers 2. Secondary Outcome Measures - Long-term Cardiovascular Risk Indicators
Optional Inclusion Criteria	Prospective imaging study 1- Women aged 18 or above 2- Women who are pregnant after 8 weeks 3- Women must be able to give written informed consent (ICF) Note: Women that are diagnosed with gestational hypertension (after 12 weeks) will be included. Includes the following hospital: NINEWELLS HOSPITAL	
Optional Exclusion Criteria	1- Maternal age less than 18 years 2- Women who are not capable of giving informed consent (ICF).	

Studying Pregnancy's VAscular and Retinal Changes (SPARC), Non CTIMP Protocol (SPARC) During Preg <v1.0 13/3/2025>; IRAS: 347685

5.Known retinal or eye disorders	 3- Pre-existing chronic hypertension or cardiovascular diseases diagnosed prior to the index pregnancy. 4. Women that have chronic hypertension at their booking visit (before 12 weeks)
hypertensive therapy, anticoagulants).	5.Known retinal or eye disorders6. Use of medications affecting endothelial function (e.g., ongoing anti-

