9 ADVERSE EVENTS

Serious Adverse A serious adverse event is any untoward medic occurrence that:	Adverse Event (AE)	Any untoward medical occurrence in a clinical research participant which does not necessarily have a causal relationship with study participation
existing hospitalisation		 results in death is life threatening requires hospitalisation or prolongation of existing hospitalisation results in persistent or significant disability or incapacity

9.1 **DEFINITIONS**

The following definitions will be used in this study, based on the American College of Obstetrics and Gynaecology (ACOG, 2002).

- 1- Chronic hypertension: BP ≥140/±90 mm Hg before pregnancy or before the 20th week of gestation
- 2- Preeclampsia-eclampsia: A pregnancy-specific disorder that is a multisystem disease characterized by hypertension ≥140/±90 mm Hg on ≥2 occasions at least 6 hours apart, and proteinuria ≥300 mg in a

24-hour urine collection, after 20 weeks' gestation. The convulsive form of PE is eclampsia and affects 0.1% of all pregnancies.

- 3- Preeclampsia superimposed on chronic hypertension: Up to 30% of women with chronic hypertension develop PE, as heralded by the occurrence of de novo proteinuria in the third trimester. In women with chronic hypertension and preexisting proteinuria (ie, before 20 weeks of gestation), the diagnosis of superimposed PE is likely with any of the following findings: sudden increase in proteinuria, sudden worsening of previously well-controlled BP, new-onset thrombocytopenia, or elevated liver function tests.
- 4- Gestational hypertension: New onset of hypertension ≥140/±90 mm Hg on ≥2 occasions at least 6 hours apart, after 20 weeks' gestation, in the absence of proteinuria, <300 mg in a 24-hour urine collection. If BP returns to normal by 12 weeks postpartum, the diagnosis of transient hypertension of pregnancy can be assigned. If elevated BP persists, the diagnosis of chronic hypertension is made.

Other conditions:

Pre-gestational diabetes

- Type I insulin-requiring diabetes
 - Participant taking (or prescribed) insulin prior to pregnancy
- Type II non-insulin requiring diabetes
 - Participant taking (or prescribed) oral diabetic agents prior to pregnancy

Gestational diabetes

- Prior pregnancy affected by gestational diabetes
 - No interval diagnosis of diabetes
- Current pregnancy affected by gestational diabetes

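### Read literally, the case-group exclusion in 3.15 bars every woman whom 3.14 requires as a case, and the case, control and synopsis exclusion lists do not agree

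*Protocol*

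**What the plan says.** Protocol 3.14 lists, among the case-group requirements, that the women "Were diagnosed with Gestational hypertension (systolic BP ≥ 140 mmHg or diastolic BP ≥ 90 mmHg) in their pregnancy". Protocol 3.15 opens with "Exclusion criteria are the same for both case and control groups" and then prints two lists. The case list includes "Women who have hypertension during pregnancy". The control list does not carry that line. It has instead a line on hypertension before pregnancy, and it adds "Women with any history of gestational hypertension", with the same blood-pressure thresholds as the case inclusion.

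Protocol 9.1 gives the definition: "Gestational hypertension: New onset of hypertension ≥140/±90 mm Hg on ≥2 occasions at least 6 hours apart, after 20 weeks' gestation". It classes hypertension before pregnancy or before week 20 as chronic.

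The synopsis has a single list for all women. It notes that women diagnosed with GH after 12 weeks are included. It excludes chronic hypertension or cardiovascular disease diagnosed before the pregnancy, chronic hypertension at the booking visit before 12 weeks, and "Use of medications affecting endothelial function (e.g., ongoing anti" (the line goes on to name antihypertensive therapy and anticoagulants).

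On grouping, 3.12 says that pregnancy outcome is documented and "participants will be placed into one of two groups retrospectively". Sections 3.2 and 6.1 also plan recruitment of women with GH through the hypertension clinic.

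**The concern.** A case must have GH in this pregnancy, and a woman with hypertension in this pregnancy may not be a case. The two rules cannot both be followed. The exclusion is not background text: 4.1 has interested women screened against the criteria by telephone or email, and 11.1 requires a departure from the protocol to be recorded and sent to the sponsor as a potential breach. Taken at its word, every GH enrolment is such a departure. If screeners set the line aside, nothing says what replaces it.

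The disagreement between the lists is a second problem. Whether a woman treated for GH is eligible depends on whether the screener reads the synopsis or 3.15, and the treatment named is one that the synopsis itself says affects endothelial function, the quantity under study. Whether a woman with GH in an earlier pregnancy is eligible may depend on her group. Both affect which women make up groups of only 11.

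**Working it through.** **Step 1. The planned case number.** Section 6.1 gives about 450 GH cases in about 4500 births per year: 450 / 4500 = 0.10. With 110 women recruited, 110 × 0.10 = 11 expected cases. This reproduces the 11 cases in 3.13 and 6.1.

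**Step 2. The case criteria as a set.**
- Inclusion (3.14): GH diagnosed in this pregnancy.
- Definition (9.1): GH is hypertension arising after week 20, hence during pregnancy.
- Exclusion (3.15, case list): hypertension during pregnancy.

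Every woman in the inclusion set lies in the exclusion set. Eligible cases = 0 of 11. Once the line is reconciled so that GH women are eligible, the expected yield returns to 110 × 0.10 = 11.

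Reading the exclusion as raised pressure on the day of the visit only does not rescue it. The text does not say so, and 6.1 wants measurements at the onset of GH.

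**Step 3. The three lists side by side.**

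| Exclusion | 3.15 case | 3.15 control | Synopsis |
|---|---|---|---|
| Hypertension during pregnancy | yes | no | no; GH women included |
| Hypertension before pregnancy | no | yes | yes |
| Chronic hypertension at booking | no | no | yes |
| History of GH | no | yes | no |
| Medication affecting endothelial function | no | no | yes |
| Recent participation in another interventional study | yes | yes | no |
| Eye disorders, age under 18, no capacity to consent | yes | yes | yes |

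The case and control lists differ on three rows, against the statement that they are the same. Section 3.14 bars cardiac disorders in both groups, which covers part of the synopsis item on cardiovascular disease. The booking-visit and medication items have no counterpart in 3.15.

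**Step 4. The gestational cut-offs.** The synopsis separates chronic from gestational hypertension at 12 weeks; 9.1 does so at 20 weeks. A reconciled list has to use one boundary.

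**Step 5. The history line.** It can be read in two ways. If it means the current pregnancy, it mirrors the case criterion (a control is not a case) and removes nobody unequally. If it means earlier pregnancies, it removes women with earlier GH from the controls and not from the cases. The documents give no rate of earlier GH and no effect of it on the retinal or Doppler measures, so the size of any resulting bias cannot be computed.

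**The case against.** The strongest reply is that this is a one-line slip with a plain intention behind it. The synopsis includes GH women, section 3 says to recruit them, 3.2 brings them in from the hypertension clinic because of their GH, and 6.1 recruits the newly diagnosed. The matching control line concerns hypertension before pregnancy, and 3.15 says that the lists are the same. All of this stands as evidence of intent. It does not remove the contradiction, because 3.15 is the rule that screeners apply and nothing says that the synopsis governs.

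A reader might infer several stronger things that the documents do not support:

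- *The study cannot recruit cases.* The figure of 0 of 11 is what the literal text implies, not a forecast.
- *Women with chronic hypertension can enter as cases, because the case list has no line on hypertension before pregnancy.* Section 9.1 keeps them out: their hypertension is not of new onset after week 20. The literal case exclusion would remove them too. What remains is a mismatch of wording.
- *Group-specific exclusions can act only after the outcome is known.* That fits women enrolled at the early scans and grouped later under 3.12. It does not fit women recruited with diagnosed GH, whose group is known at entry. GH in an earlier pregnancy is also known at enrolment.
- *The control-only history line biases the contrast away from zero by a known amount.* This depends on the second reading in Step 5. Even then, choosing controls without earlier GH can be defended as a choice of contrast, provided that it is deliberate and stated.

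It is also fair to say that 5.1 already collects medical history and medications, and 6.2 already plans adjustment for pre-existing health conditions. No new data item is needed.

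**Conclusion.** The protocol is wrong as written. The case exclusion in 3.15 negates the case inclusion in 3.14, given the definition in 9.1: 0 of 11 cases are eligible on the literal text, against 11 expected once the line is reconciled. This part rests on no assumption beyond the wording. The claim in 3.15 that the lists are identical is false on three items, and the synopsis exclusions for booking-visit hypertension and medication are absent from 3.15.

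The history-of-GH line is a lesser point and a conditional one. If it refers to earlier pregnancies and applies to controls only, it could make the controls selectively lower-risk. That is a possible bias whose size the documents do not allow anyone to state.

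The eligibility conflict must be settled before screening relies on 3.15. The remaining mismatches belong in the same amendment.

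**What to change.** 1. Reconcile 3.14, 3.15 and the synopsis into one exclusion list that does not exclude the GH cases. The parallel control line and the opening sentence of 3.15 suggest that the case line was meant to concern hypertension before pregnancy; the sponsor should confirm this. Substituting that line alone is not enough: the list must also agree with the booking-visit item in the synopsis and with the 9.1 definition, including the 12- and 20-week boundaries.
2. State whether "Women with any history of gestational hypertension" means the current pregnancy or earlier ones. If earlier ones, apply it to both groups or to neither, and use the medical history collected under 5.1 to describe or adjust for earlier GH.
3. Reconcile the medication exclusion in the synopsis with 3.15 and with recruitment from the hypertension clinic. This review does not say which rule is right. Whichever is kept, report antihypertensive use at the scan, by group, from the medication data already collected.
4. Correct the sentence that the lists are the same, or make it true.

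The cost is amendment wording and its approval, with no new data collection. If controls with earlier GH are kept, the case-control contrast may be slightly smaller.
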